3.9 Dual antiplatelet therapy in elderly patients

In the SENIOR trial (12), elderly patients undergoing PCI were treated with a short DAPT regimen ranging from 1 to 6 months. Roughly 50% of patients DAPT was interrupted at 1 month with a good clinical outcome in the overall population. In addition, age ≥ 75 years is one of the criteria for high-bleeding risk in all bleeding risk scores such as PARIS Bleeding score and PRECISE-DAPT score. Thus, elderly patients with MI

and multivessel disease are both at high- ischemic and bleeding risk and the balance between these two competing risks is particularly complex. Due to this reason and to the results of the SENIOR trial, a stent with biodegradable polymer is the standard of care in this subset of patients. In fact, a relevant portion of patients will have to limit DAPT duration as much as possible due to clinical events or high-bleeding risk.

4 RATIONALE

Elderly patients presenting with MI and multivessel disease are the highest risk population with the worst prognosis. No trial has ever been designed to optimize their outcome. The actual real-life standard of care is, in the best of the cases, culprit only revascularization. However, real-life registries show that outcome of ACS elderly patients treated with this strategy is far from being optimal with at least a 15% rate of cardiac death or myocardial infarction at 1 year.

To date, studies on this population have been focused on devices (BMS vs biodegradable DES) or on DAPT (long vs short) and no study was focused on evaluating if complete revascularization is able to improve the prognosis in these patients. The contemporary complete revascularization is represented by a functionally-driven revascularization that recently showed to significantly reduce myocardial infarction rate and outperformed an angio-complete revascularization. Thus, our hypothesis is that a functionally-driven complete revascularization in elderly patients with MI and multivessel disease may improve prognosis compared to the actual standard of care in these patients, namely culprit only revascularization. Being a “strategy” trial, we identified the patient-oriented composite endpoint (POCE) as primary outcome of interest (all cause death, any MI, any stroke, any revascularization) (43).

5 STUDY OBJECTIVES

5.1 Primary objective

- To test if a functionally-driven complete revascularization is superior to a culprit only strategy in the reduction of the POCE of all-cause death, any MI, any stroke, any revascularization at 1 year in elderly patients with MI and multivessel PCI

5.2 Main Secondary objectives

- To test if a functionally-driven complete revascularization is superior to a culprit only strategy in the reduction of POCE of all-cause death, any MI, any stroke, any revascularization at 3 and 5 years
- To test if a functionally-driven complete revascularization is superior to a culprit only strategy in the reduction of the device oriented composite endpoint (DOCE) of cardiovascular (CV) death, MI or non-culprit target vessel revascularization (TVR) at 1, 3 and 5 years
- To test if a functionally-driven complete revascularization is superior to a culprit only strategy in the reduction of the composite endpoint of cardiovascular death or MI at 1, 3 and 5 years
- To test if a functionally-driven complete revascularization is superior to a culprit only strategy in the reduction of the composite endpoint of death or MI at 1, 3 and 5 years
- To test if a functionally-driven complete revascularization is superior to a culprit only strategy in the reduction of all the single components of the POCE and DOCE at 1, 3 and 5 years
- To evaluate the rate of ischemic adverse events in patients interrupting DAPT
- To evaluate the rate of ischemic adverse events in patients disrupting DAPT
- To test if a functionally-driven revascularization is non-inferior to a culprit only revascularization strategy in Contrast-Induced Acute Kidney Injury (CI-AKI) rate

5.3 Exploratory endpoints

- To test if a functionally-driven complete revascularization is superior to a culprit only strategy in the reduction of ischemia driven revascularization at 1, 3 and 5 years

[figure not shown]
- To test if non-invasive functional strategy based on QFR evaluation is superior to a culprit only strategy in terms of target lesion failure (TLF) at 1, 3 and 5 years
- To test if functional strategy based on AFI evaluation is superior to a culprit only strategy in terms of target lesion failure (TLF) at 1, 3 and 5 years
- To test if non-invasive functional strategy based on QFR evaluation is superior to a culprit only strategy in terms of ischemia-driven revascularization at 1, 3 and 5 years
- To test if functional strategy based on AFI evaluation is superior to a culprit only strategy in terms of ischemia-driven revascularization at 1, 3 and 5 years
- To test if non-invasive functional evaluation (QFR) is non-inferior to an invasive functional strategy (FFR, iwFR, cFFR) in terms of target lesion failure (TLF) at 1, 3 and 5 years
- To test if functional evaluation with AFI is non-inferior to an invasive functional strategy (FFR, iFR, cFFR) in terms of target lesion failure (TLF) at 1, 3 and 5 years
- To test if non-invasive functional evaluation (QFR) is non-inferior to an invasive functional strategy (FFR, iwFR, cFFR) in terms of ischemia driven revascularization at 1, 3 and 5 years
- To test if functional evaluation AFI is non-inferior to an FFR guided strategy in terms of ischemia driven revascularization at 1, 3 and 5 years
- To test if a functionally-driven complete revascularization is superior to a culprit only strategy in terms of quality of life measured with EQ-5D quality of life scale at 1, 3 and 5 years
- To test if a functionally-driven complete revascularization is superior to a culprit only strategy in terms of physical performance measured with short physical performance battery (SPBB) at 1, 3 and 5 years
- To test if a functionally-driven complete revascularization is superior to a culprit only strategy in terms of angina symptoms control measured with Seattle Angina Questionnaire (SAQ) Frequency scale at 1 year

6 STUDY DESIGN, SCREENING AND RANDOMIZATION

6.1 Study design

All comers, prospective, randomized, multicenter, open-label trial with blinded adjudicated evaluation of outcomes (PROBE).

6.2 Study flow chart

6.3 Screening

All patients undergoing CAA because of MI must be screened for eligibility. Patient's eligibility must be assessed after the evidence of multivessel disease at CAA amenable for PCI with a clear culprit lesion. After eligibility is confirmed, written informed consent must be obtained prior to randomization. Successful culprit lesion treatment must be obtained in all patients before randomization. The suggested stent for culprit lesion treatment is DES with degradable polymer. In STEMI setting, it is possible to enroll the patient also after the successful primary PCI due to the possible difficulty to obtain an informed consent in the setting of STEMI. Key baseline patient characteristics (i.e., inclusion/exclusion criteria, demographics, medical history, details of cardiovascular anatomy, ECG and laboratory test results) will be recorded on the electronic Case Report Forms (eCRF). All CAA from the initial qualifying PCI as well as all functional assessments will be collected and forwarded to an angiographic core lab for further assessment.

6.4 Randomization

Randomization will be performed after CAA and culprit lesion treatment. Randomization will be performed centrally using an internet-based system. The patient identification number (Patient ID) and the treatment allocation will be assigned by the central randomization system. Treatment allocation will be assigned according to a computer generated randomization list stratified by center. Randomization will also be stratified by sex and clinical presentation (STE vs NSTEMI). All patients who are randomized are irrevocably in the study, whether or not they are subsequently found to be eligible, or actually receiving the allocated treatment. Therefore, all patients must be followed until the pre-specified study end date.

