8 STUDY PROCEDURES

8.1 Management Strategies

After CAA and before randomization, Operator must indicate the culprit lesion and all diseased vessels (based on % stenosis at visual estimation). This information must be reported in eCRF before randomization.

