10 STATISTICAL ANALYSIS PLAN

All statistical analyses will be performed by the Centro di Ricerca Clinica ed Epidemiologica of the University of Ferrara under the supervision of [name]. Analysis will be performed on an Intention to Treat (ITT) set, defined as all intentionally randomized patients, by randomization treatment. Supportive per-protocol analyses will be performed on the primary and key secondary endpoints. A detailed statistical analysis plan will be completed before the end of the study. In brief, continuous variables will be tested for normal distribution with the Kolmogorov-Smirnov test and with visual estimate of Q-Q plot. Normally distributed variables will be presented as mean±SD and compared by t test and 1-way ANOVA. Otherwise, median [inter-quartile range], Mann-Whitney U and Kruskal-Wallis tests will be used. Categorical variables will be summarized in terms of absolute and relative frequencies (percentages) and compared by using χ^2 test. One-sided tests will be done in order to check the superiority of functionally-driven complete revascularization. Statistical significance will be set at $\alpha=0.05$ level. Formal type-I error control will be ensured for the primary and the key secondary endpoint by a sequential procedure where significance for the key secondary endpoint is accepted only if the primary endpoint is positive. Kaplan-Meier curves will be plot to describe survival free from adverse events, and difference between groups will be test will log-rank test. The primary analysis will be based on events of all follow-up time of each patient at the time of the database lock. Further analyses will be performed with events after more than 30 days considered as censored, as well as after more than 365 days considered as censored. Any confounding factor will be tested by Cox regression models. Variables with a p-value <0.1 at univariate analysis will be entered into a multivariable analysis to identify the independent predictors. When appropriate, 95% CI will be calculated. In addition, we will assess the composite primary outcome POCE (all-cause mortality, any MI, any stroke and any revascularization) with the use of the Finkelstein–Schoenfeld method, which is based on the principle that each patient in the clinical trial is compared with every other patient in a pairwise manner. This method gives a higher importance to all-cause mortality. The pairwise comparison proceeds in hierarchical fashion, using all-cause mortality, followed by frequency of MI when patients cannot be differentiated on the basis of mortality and so on for the other endpoints We will apply the Finkelstein–

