
Schoenfeld method to the patients stratified according to clinical presentation (STE vs NSTE) and number of diseased vessels (2 vs 3), yielding four stratification pools. All analyses will be performed with STATA 13 (StataCorp, College Station, TX).

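### Randomization is stratified by center, sex and presentation, but the log-rank comparison names no strata and the Cox covariates are chosen by univariate p<0.1

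*Protocol*

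**What the plan says.** Protocol section 6.4 (Randomization) sets three stratification factors. The first is center: "Treatment allocation will be assigned according to a computer generated randomization list stratified by center". The other two follow: "Randomization will also be stratified by sex and clinical presentation (STE vs NSTEMI".

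Protocol section 10 (Statistical analysis plan) describes three analyses that could use these factors:

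- **Log-rank.** For survival free from adverse events, "difference between groups will be test will log-rank test". No strata are named.
- **Cox regression.** "Any confounding factor will be tested by Cox regression models", and then "Variables with a p-value <0.1 at univariate analysis will be entered into a multivariable analysis to identify the independent predictors". No variable is retained regardless of its p-value.
- **Finkelstein-Schoenfeld.** This additional analysis of the primary composite is "stratified according to clinical presentation (STE vs NSTE) and number of diseased vessels (2 vs 3), yielding four stratification pools". Presentation is kept, sex and center are absent, and vessel number is added.

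Section 8.1 requires the operator to identify the culprit lesion and all diseased vessels after angiography, and says of this: "This information must be reported in eCRF before randomization". Section 10 presents its methods as a short summary and defers a detailed statistical analysis plan to a later date. That plan is not at hand.

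**The concern.** When allocation is balanced within prognostic strata, the analysis should normally condition on the same strata. An unstratified test does not credit the balance the design has created, so its variance is slightly too large and some power is lost. Nothing in section 10 links the randomization factors to the analysis, and the one analysis with named strata uses a different set.

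The screening rule raises a second issue. The log-rank test gives no effect estimate, and Cox regression is the only model in section 10 that could supply a hazard ratio. If the treatment hazard ratio came from the screened model, its covariates would be chosen by the trial's own outcomes. Sex or presentation could drop out while unrelated variables entered, and the usual 95% confidence interval would take no account of that selection. In an open-label trial it is also worth limiting analytic discretion in advance.

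**Working it through.** **1. Factors side by side**

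| Step | Center | Sex | Presentation | Vessel number |
|---|---|---|---|---|
| Randomization (6.4) | yes | yes | yes | no |
| Log-rank (10) | not named | not named | not named | not named |
| Cox (10) | not retained by rule | only if p<0.1 | only if p<0.1 | only if p<0.1 |
| Finkelstein-Schoenfeld (10) | no | no | yes | yes |

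**2. The plan's own sample size**

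Inputs from section 10.1: control risk 15%, relative reduction 30% (so 10.5%), power 80%, 5% level. Section 10 makes the tests one-sided. Allocation of 1:1 is assumed, because no ratio is given.

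n per arm = [z(0.95)·√(2·p̄·(1−p̄)) + z(0.80)·√(p1(1−p1) + p2(1−p2))]² / (p1−p2)², with p̄ = 0.1275

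= [1.645 × 0.4717 + 0.842 × 0.4706]² / 0.045² = 678.2, rounded up to 679

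The total is 1358, an exact match. Attrition: 1358 × 1.02 = 1385.2, against the stated 1385. Stratifying the test does not alter this figure.

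**3. What stratifying the log-rank test buys**

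The hazard ratio matching 15% against 10.5% is ln(0.895)/ln(0.85) = 0.683. The simulation used 1386 patients, allocation balanced within sex by presentation, exponential times censored at 1 year, a one-sided 5% test and 10,000 trials per cell. Three inputs are assumptions, because the protocol gives none: 36% women, 35% STEMI, and the prognostic hazard ratios below.

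| Assumed HR, presentation / sex | Power, unstratified | Power, stratified | Type I error, unstratified | Type I error, stratified |
|---|---|---|---|---|
| 1 / 1 | 81.1% | 80.9% | 4.8% | 4.9% |
| 1.5 / 1.3 | 80.2% | 80.4% | 5.3% | 5.4% |
| 2 / 1.5 | 80.8% | 81.3% | 4.8% | 5.0% |
| 3 / 2 | 80.0% | 81.3% | 4.6% | 5.2% |

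The Monte Carlo standard error is √(0.05 × 0.95/10,000) = 0.2 points for type I error and √(0.8 × 0.2/10,000) = 0.4 points for power. A smaller simulation (1358 patients, 3,000 trials per scenario) agrees. Power rose from 81.2% to 81.8% with assumed hazard ratios of 1.5 and 2.0 for the two factors, and from 81.8% to 83.1% with 1.5 and 3.0. At 1.3 there was essentially no change.

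**4. What p<0.1 screening does**

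- *Unrelated variables let in.* With k unrelated candidates, 0.10 × k are expected to pass: 1 of 10, 2 of 20, 3 of 30. The protocol lists no candidates, so k is an assumption.
- *A randomization factor lost.* Expected 1-year events under the plan are 679 × (0.15 + 0.105) = 173. With 36% women, the standard error of the log hazard ratio for sex is about 1/√(173 × 0.36 × 0.64) = 0.158. If the true hazard ratio for sex were 1.3, then ln(1.3)/0.158 = 0.262/0.158 = 1.66, almost the same as the two-sided 10% critical value of 1.645. Sex would therefore enter the model in only about half of such trials.

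**The case against.** Section 10 is a summary with a detailed plan to follow, and whether a log-rank test is stratified is often settled in that later document. The protocol never says the test is unstratified, nor does it attach the word primary to it. This stands as a caution: the log-rank part rests on an omission. The omission still carries weight, because the same section does name strata for another analysis of the same endpoint. The screening rule and the Finkelstein-Schoenfeld strata are explicit text.

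Four stronger readings are tempting, and the document does not support them.

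- *The primary test is invalid.* It is not. In the simulations, unstratified type I error ran from 4.6% to 5.3%, and power stayed at 80% or above in every scenario.
- *The Finkelstein-Schoenfeld strata are wrong because vessel number was not a randomization factor.* Stratifying by a factor recorded before randomization is valid, and section 8.1 requires that recording.
- *The 2 versus 3 split leaves some patients without a stratum.* This needs inclusion criterion 3 to admit a non-culprit lesion in the culprit vessel. The criterion is framed as multi-vessel disease, so that is only one possible reading.
- *The trial's main hazard ratio has an invalid interval.* The screen's stated purpose is to find independent predictors. No adjusted hazard ratio is declared to be the primary estimate, so the problem is conditional on such use.

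**Conclusion.** The point holds as a matter of efficiency and consistency. The analysis as described does not carry forward the factors used to randomize. For the log-rank test the cost is about 0 to 1.3 points of power, and the upper end needs an assumed threefold effect of presentation. Type I error is not inflated and N = 1358 is unaffected. These sizes rest on assumed stratum prevalences and prognostic effects and on 1-year censoring.

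The screening rule is the part that most needs closing. As a search for predictors it is harmless to the main conclusion. As a route to the treatment effect it would make the estimate depend on outcome-driven selection, and section 10 names no other adjusted model that would rule out this use.

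**What to change.** In section 10 and in the detailed statistical analysis plan:

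1. Stratify the primary log-rank test by sex and clinical presentation.
2. Take the treatment hazard ratio from a Cox model stratified by the same two factors, with center handled as a random or clustering effect.
3. For any further adjusted treatment effect, fix the covariate list in advance. Age and number of diseased vessels are natural candidates, as both are known before randomization.
4. Limit the p<0.1 screen to exploratory analysis of predictors, and say so.
5. Optionally, add sex to the Finkelstein-Schoenfeld strata, or give the reason for using vessel number instead.

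The cost is wording. The variables are already collected, the sample size does not change, and the edit can be made before any unblinded data are seen.

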7 STUDY POPULATION

7.1 Inclusion criteria

1. Patients \geq 75 years **AND**
2. MI (STE or NSTEMI) with indication to invasive management **AND**
3. Multi-vessel disease defined as at least 1 non-culprit coronary artery lesion at least 2.5 mm in diameter deemed at visual estimation with a diameter stenosis % ranging from 50 to 99% amenable to successful treatment with PCI **AND**
4. Successful treatment of culprit lesion

7.2 Exclusion criteria

1. Planned surgical revascularization
2. Non-cardiovascular co-morbidity reducing life expectancy to $<$ 1 year
3. Any factor precluding 1-year follow-up
4. Prior Coronary Artery Bypass Graft (CABG) Surgery
5. Impossibility to identify a clear culprit lesion
6. Left Main lesion as non-culprit

8 STUDY PROCEDURES

8.1 Management Strategies

After CAA and before randomization, Operator must indicate the culprit lesion and all diseased vessels (based on % stenosis at visual estimation). This information must be reported in eCRF before randomization.

8.1.1 General information regarding revascularization

Drug eluting stents with biodegradable polymer with struts $\leq 65 \mu$ should be implanted. If feasible, each patient should receive revascularization with a single stent brand. Considering the outcome data and the technical characteristics, it is highly suggested to utilize Supraflex stent or its newer versions. All patients must be treated with low dose ASA and P2Y12 inhibitor (Ticagrelor unless contraindicated). The use of a glycoprotein IIb/IIIa inhibitor is left to the discretion of the operator. The use of heparin, bivalirudin or low molecular heparin for procedural anticoagulation is also left to the discretion of the investigator. Radial approach is strongly recommended. Presence of Chronic Total Occlusion (CTO) is not an exclusion criterion per se, although, it is needed another non culprit lesion $\geq 50\%$ to randomize the patient.

8.1.2 Culprit-only Revascularization Strategy

All patients randomized to culprit only revascularization must not undergo PCI any lesion except from the culprit lesion already treated at the moment of the randomization. Staged procedures are considered protocol violation.

8.1.3 Complete Revascularization Functionally-guided

Patients who are randomized to this strategy will receive revascularization of the culprit lesion and guided by functional assessment on all non-culprit lesions. Functional evaluation is mandatory for all stenosis with diameter stenosis % between 50 and 90% at visual estimation, while it is suggested but not mandatory for all stenosis between 91 and 99%. Revascularization must be guided by functional assessment on all vessels. The system utilized to obtain functional evaluation is left to Operator's discretion. FFR, iwFR, cFFR and QFR

are all allowed. PCI is allowed only if functional evaluation is positive according to the threshold of the chosen functional system. PCI of vessel with negative functional evaluation is considered a protocol violation. Drug eluting stents with biodegradable polymer with struts $\leq 65 \mu$ must be implanted in all non-culprit lesions with positive functional assessment. Routine stress testing and repeat angiography are not indicated in patients whose symptoms are stable. CTO management in the complete revascularization group is left to the Operators' discretion according to the clinical practice of his/her Institution. It is suggested to achieve functional complete revascularization within the index procedure, while it is mandatory to obtain it within the index hospitalization.

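### Section 8.1.3 makes functional testing optional for 91-99% non-culprit stenoses but allows PCI only after a positive test, so the experimental strategy contradicts itself for an untested 91-99% lesion

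*Protocol*

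**What the plan says.** Section 8.1.3 of the Protocol defines the experimental strategy. It opens by describing revascularization as "guided by functional assessment on all non-culprit lesions". It then sets two testing bands by visual stenosis:

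- 50-90%: "Functional evaluation is mandatory for all stenosis with diameter stenosis % between 50 and 90% at visual estimation".
- 91-99%: "it is suggested but not mandatory for all stenosis between 91 and 99" per cent.

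Two general sentences follow. The first is "Revascularization must be guided by functional assessment on all vessels". The second, after the permitted systems are listed, is "PCI is allowed only if functional evaluation is positive according to the threshold of the chosen functional system". The section then classes PCI of a vessel with a negative evaluation as a protocol violation and requires stents in non-culprit lesions with a positive one. Chronic total occlusions get their own sentence, which begins "CTO management in the complete revascularization group is left to the" and hands the decision to the operator and local practice. The section ends by making functional complete revascularization mandatory within the index hospitalization.

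Three other places bear on this. Section 7.1 accepts a non-culprit lesion with "diameter stenosis % ranging from 50 to 99% amenable to successful treatment with PCI". Section 10 plans supportive per-protocol analyses of the primary and key secondary endpoints. Section 13 has the core lab review the functional evaluation of all stenoses, with retraining of a center and a possible stop to enrollment if evaluation is poor.

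**The concern.** An operator who uses the option not to test a 91-99% lesion has no positive result. The permission sentence then bars PCI of that lesion, while the testing sentence says the operator did nothing wrong by not testing. The section never says what is to be done with the lesion.

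What is at stake is the definition of the experimental treatment. One site can leave the untested lesion alone because no positive test exists. Another can treat it because testing was optional. Each can point to a sentence in the same section. Where that lesion is the patient's only qualifying one, the ambiguity covers the whole of the assigned non-culprit treatment. It also arises in one arm only, since section 8.1.2 gives the culprit-only arm a plain rule. Adherence in the experimental arm therefore has no fixed meaning for these lesions, and neither the per-protocol analyses nor the core-lab review has a rule to apply to them.

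**Working it through.** This point rests on comparing sentences, so the plan's only related figure is checked first to show that it does not enter.

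**Sample size (section 10.1).** Inputs: control rate 15%; 30% relative reduction, giving 0.15 × 0.70 = 0.105; 80% power; 5% level, one-sided per section 10. The pooled two-proportion formula without continuity correction is

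n per arm = [z₀.₉₅ √(2p̄(1−p̄)) + z₀.₈₀ √(p₁(1−p₁) + p₂(1−p₂))]² / (p₁−p₂)²

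with p̄ = (0.15 + 0.105)/2 = 0.1275. The first root is √0.2225 = 0.4717 and the second is √0.2215 = 0.4706. The numerator is (1.645 × 0.4717 + 0.842 × 0.4706)² ≈ 1.373 and the denominator is 0.045² = 0.002025. This gives about 678.2, rounded up to 679 per arm, or 1358 in total. The plan's figure is reproduced, and nothing from section 8.1.3 is used in it.

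**What each sentence says about a 91-99% lesion that was not tested.**

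| Sentence | Applied to an untested 91-99% lesion |
|---|---|
| 7.1, qualifying range 50-99% | The lesion can qualify the patient |
| 8.1.3, testing bands | Not testing is allowed |
| 8.1.3, guidance on all vessels | Not testing is not allowed; no exception stated |
| 8.1.3, PCI only if positive | PCI is not allowed; no exception stated |
| 8.1.3, violation sentence | Silent: names only vessels with a negative evaluation |
| 8.1.3, stent sentence | Silent: names only lesions with a positive assessment |
| 8.1.3, completion in hospital | Does not say whether leaving the lesion counts as complete |
| 13, core-lab review | No rule for a stenosis without an evaluation |

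The second and third rows conflict directly. The second and fourth rows together mean that a permitted omission removes permission to treat. The fourth and fifth rows mean that treating the lesion breaks a stated rule without being a stated violation.

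**CTO.** Section 8.1.1 allows patients with a CTO to enter if another non-culprit lesion of at least 50% is present, so this case can also occur. The testing bands stop at 99%, so a CTO lies outside them and has a sentence of its own. Nothing says whether that sentence overrides the PCI permission rule.

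**Size.** The protocol gives no frequency for 91-99% non-culprit lesions, for how often they go untested, or for treated CTOs. No effect on the per-protocol set or on the treatment contrast can be calculated from it.

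**The case against.** The strongest reply is that the section makes sense when read in order. The bands come first. The permission sentence refers to the threshold of a chosen system, which presupposes that a test was done, and the sentence after it targets PCI after a negative test. On this reading a result binds wherever a test was performed, and where testing is optional the operator may proceed without one. Leaving the tightest lesions untreated would also sit oddly with an arm described as complete revascularization. This reading is plausible and may be what was meant. However, it needs an exception that neither general sentence contains, and it goes against the plain sense of a rule that permits PCI only on a positive result. A rule that sites must follow should not depend on that inference.

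Three parts of the reply stand.

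- The CTO sentence reads naturally as a specific exception. It needs one clarifying clause and is not a second contradiction of equal weight.
- Much of the recording is already planned. Section 8.1 has the culprit lesion and all diseased vessels, by visual stenosis, entered in the eCRF before randomization, and section 13 has the core lab review stenosis and functional evaluation.
- The composition of the per-protocol set is properly left to the statistical analysis plan, and its absence here is not a fault.

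A reader might also infer that per-protocol exclusions will strip the most severe disease from the experimental arm. The protocol does not support that: it lists only PCI after a negative evaluation as a violation and gives no per-protocol exclusion rule. Such one-sided loss is possible only if treated untested lesions are later counted as deviations.

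**Conclusion.** The contradiction is real as written and limited to one case: an untested 91-99% non-culprit lesion in the complete-revascularization arm. It rests on the wording of section 8.1.3 and on the qualifying range in section 7.1, and on no numerical assumption. The intention-to-treat primary analysis set, by randomized arm, and the derivation of 1358 patients are unaffected.

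A reader might go further and convert the ambiguity into lost power for the primary comparison. That would need a share of patients with such lesions, the proportion left both untested and untreated, and a complete loss of benefit in those patients even when their other lesions are treated. The protocol supplies none of these, so no power figure is justified. The supportable conclusion is that the delivered strategy and adherence to it are undefined for these lesions, by an amount that cannot be stated.

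**What to change.** Amend section 8.1.3 so that the testing bands, the all-vessels sentence, the PCI permission sentence and the violation sentence express one rule for untested 91-99% lesions. The rule itself is a clinical decision for the sponsor. Add a clause saying whether the CTO discretion sentence is an exception to the PCI permission sentence.

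Use the same rule for listing protocol violations, for judging adherence in the per-protocol analyses, and for the core-lab review in section 13. To make this workable, add to the eCRF a flag for each non-culprit lesion showing whether it was tested and whether it was treated. The visual stenosis is largely captured already.

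The cost is a short clarifying amendment to one section and a small eCRF addition. The sample size and the primary analysis need no change.
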